8.1.8.1 Daily eDiary

During the study period, participants will be required to take their asthma controller therapy regularly and complete an eDiary twice daily.

At SV1, participants will receive a handheld eDiary device to complete twice-daily, daily and non-daily PRO assessments during the study. Participants will be provided training on the use of the handheld device. Daily assessments will include night-time and daytime asthma symptoms (morning and evening diary, respectively), use of inhaled rescue medication in response to worsening symptoms, nights with awakenings due to asthma symptoms (morning diary only) and background medication use. The PEF data (obtained from the home peak flow meter) will be captured at the conclusion of the morning and evening eDiary entry.

Daytime is defined as the time period between the morning lung function assessment (upon rising in the morning) and the evening lung function assessment. Night-time is defined as the time period between the evening lung function assessment (at bedtime) and the morning lung function assessment.

The number of doses of rescue medication (1 dose unit = 1 puff on inhaler) taken will be recorded by the participant in the eDiary twice daily. The number of inhalations taken between the morning and evening lung function assessments will be recorded in the evening. The number of inhalations taken between the evening and morning lung function assessments will be recorded in the morning.

Nocturnal awakenings due to asthma symptoms will be recorded by the participant in the daily eDiary each morning by answering the question whether he/she woke up during the night due to asthma symptoms by a “yes” or “no” response.

Background (inhaled ICS/LABA) medication administration use will be recorded once daily in the daily eDiary as “yes” or “no” response.

The eDiary questions support the analysis of a novel endpoint called CompEx (Section 8.1.6).

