3 PRIMARY AND SECONDARY VARIABLES

3.1 General principles

3.1.1 Baseline definitions

In general, the last measurement prior to first injection of IP will serve as the baseline measurement for efficacy and safety endpoints. If Visit 4 (Day1) measurement is missing, the last non-missing value before Visit 4 (Day 1) will be used as baseline instead. If there is no result collected prior to Visit 4, then baseline value will be set to missing and will not be imputed. In the scenario where there are two assessments on Visit 4 (Day 1) prior to first dose, one with time recorded and the other without time recorded, the one with time recorded would be selected as baseline.

An exception from the general rule will be ECGs. The mean value of each parameter from the triplicate measurements at Visit 4 (Week 0) pre-dose will be used as the baseline value.

For bi-weekly summaries, such as 2-weekly mean number of night-time awakenings, 2-weekly mean daily rescue medication usage, 2-weekly mean FEV1, 2-weekly mean PEF,

baseline would be defined as the mean from last 2 weeks (14 days) results before Visit 4 (Week 0), ie from evening of Study Day -14 to the morning of Study Day 1. If there are fewer than 10 completed days in the 14-day baseline period (where a complete day = entry from the evening AND the following morning) then baseline will be set to missing.

For CompEx analysis the mean from last 2 weeks (14 days) results before Visit 4 (Week 0) should be derived separately for morning and evening assessments. If there are fewer than 7 completed days in the 14-day baseline period (where a complete day = entry from the evening AND the following morning) then baseline for CompEx event will be set to missing. To note: PEF is expected to be collected with 3 measurements for each morning and evening assessment. The maximum value provided by the vendor (both morning and evening for the 2-weekly mean analysis and separately for the CompEx analysis) should be used to derive the baseline and any post-baseline assessments.

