Period 4: Evening of Day 43 – Morning of Day 57	Week 8	57
Period 5: Evening of Day 57 – Morning of Day 71	Week 10	71
Period 6: Evening of Day 71 – Morning of Day 85	Week 12	85
Period 7: Evening of Day 85 – Morning of Day 99	Week 14	99
Period 8: Evening of Day 99 – Morning of Day 113	Week 16	113
Period 9: Evening of Day 113 – Morning of Day 127	Week 18	127
Period 10: Evening of Day 127 – Morning of Day 141	Week 20	141
Period 11: Evening of Day 141 – Morning of Day 155	Week 22	155
Period 12: Evening of Day 155 – Morning of Day 169	Week 24	169

The Early Discontinuation and unscheduled visits will be included when applying the visit windows to ensure that all available data are used in the analysis.

For bi-weekly summaries, the mean of all non-missing observations within an assigned window is calculated. If there are fewer than 10 completed days in the 14 day period (where a

complete day = entry from the evening AND the following morning) then the analysis value will be set to missing.

Finally, for the purpose of the statistical analysis, the assessments will be allocated to the study phase in which they are collected as reported below.

Table 2 Study phase windows

Study phase	Phase Window for Analysis (Days)
Pre-treatment	Prior to the first administration of investigational product (day <1 ^a)
On-treatment	≥ day 1 ^b to last dose date plus 28 days (included)
Follow-up	> last dose date plus 28 days

^a Includes all measurements collected before first dose of IP. If the measurement is collected on day 1 it cannot be determined if it was done before or after the first dose of IP (due to missing time and/or planned time point), then it will be considered as collected after first dose of IP.

^b Includes all measurements collected on the day of first dose of IP, at the time of IP intake and after.

Unless otherwise specified, the study phase will be mainly used for safety analysis (e.g., laboratories, adverse events) and for CompEx analysis.

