3.6.2 Patient reported outcome (PRO) variables

Patient-reported outcome data will be captured via an ePRO device. For all outcomes based on the ePRO devices, analyses will be based on data up to and including Week 24.

For asthma symptom score, rescue medication use and home peak expiratory flow, 2-weekly means will be calculated. A 2-weekly mean is calculated as the sum of all non-missing daily measures/scores over 14 sequential days divided by the number of days with non-missing measures/scores. For nights with awakenings due to asthma, the 2-weekly mean will be the percentage of times the participant answered “yes” to ‘did your asthma cause you to wake up’ and “yes” to ‘did you use rescue medication upon awakening’. For derivation of the 2-weekly mean scores see Section 3.1.4. Note that the first 2-weekly mean in the treatment period will be based on the evening recording on day 1 up to and including the morning recording on day 15. The daytime score is recorded in the evening and the night-time score is recorded the following morning; 2-weekly periods are defined as follows (where Day 1 is the day of randomisation)

Where a total score is calculated within a day (e.g. Asthma symptom score), this calculation will span two calendar days – the daytime value recorded in evening of day X, and the night-time value recorded on morning of day x+1. E.g. the asthma symptom score on Day 1 will be the day time score recorded on the evening of Day 1 + the night-time score recorded on the morning of Day 2.

Where only night-time scores/results are of interest, the morning entries on the second day of a period up to and including the morning entry on the last day of the period (or morning of the last day of study for the last period/last IP intake) will be considered. Where only daytime scores/results are of interest, the evening entries on the first day of the period up to and including the evening entry on the second last day of the period (or evening before the last day of study/last IP intake) will be considered.

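### The 10-of-14 paired-day rule for 2-weekly diary values also governs endpoints built from one entry per day, so observed data for night-time awakenings and the separate day and night symptom means can be set to missing

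*SAP*

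**What the plan says.** SAP 3.1.4 gives one completeness rule for all bi-weekly summaries after baseline. It begins "If there are fewer than 10 completed days in the 14 day period (where a" and continues "complete day = entry from the evening AND the following morning) then the analysis value will be set to missing". When the threshold is met, "the mean of all non-missing observations within an assigned window is calculated", so entries from incomplete days are then used.

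SAP 3.1.1 applies the same rule before treatment: "If there are fewer than 10 completed days in the 14-day baseline period", on the same pairing, baseline is missing. The scope is explicit: "For bi-weekly summaries, such as 2-weekly mean number of night-time awakenings, 2-weekly mean daily rescue medication usage" head the list, followed by 2-weekly mean FEV1 and PEF.

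Protocol 8.1.8.1 lists, among the daily assessments, "nights with awakenings due to asthma symptoms (morning diary only"), and adds: "Nocturnal awakenings due to asthma symptoms will be recorded by the participant in the daily eDiary each morning". SAP 3.6.2 says which entries feed single-entry results. For nights it reads: "Where only night-time scores/results are of interest, the morning entries on the second day of a period up to and including the morning entry" of the last day. Daytime results correspondingly use evening entries. That section refers back to 3.1.4 for the derivation and sets no separate minimum. SAP 3.6.2.1 makes the daily symptom total the outcome variable, and also plans separate 2-weekly daytime and night-time symptom means.

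**The concern.** The completeness test and the data used do not match for three variables: night-time awakenings, the night-time symptom mean (both morning only) and the daytime symptom mean (evening only). A missing entry that the variable never uses can cause the observed entries to be discarded. Neither document exempts single-entry variables.

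For these variables the rule can also rank records the wrong way round. Fourteen mornings with nine evenings is rejected, while ten mornings that are all paired is accepted, although the first record holds four more nights of data.

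What is at stake is precision in exploratory mixed-model (MMRM) analyses through Week 24 (SAP 4.2.6.6). SAP 3.1.5 justifies that model on the ground that it uses whatever data are available. Deleting observed values beforehand works against that aim.

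**Working it through.** The plan gives no figure of its own to reproduce here. The check is a count, followed by an illustration under stated assumptions.

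**Count.** The number of completed days cannot exceed the smaller of the morning and evening counts. With 14 mornings and 9 evenings there are at most min(14, 9) = 9 completed days. Since 9 < 10, the value is set to missing with all 14 nights observed.

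**Does pairing protect anything for these variables?** Set side by side, the sections suggest not. SAP 3.1.4 averages unpaired entries once the threshold is met, so pairing is not a condition on what enters the mean. Where both halves are needed, SAP 3.6.2.1 already sets a day's symptom total to missing if either half is absent.

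**Illustration.** Inputs: 14 days and a threshold of 10 (SAP 3.1.4); probability p that any one entry is made (assumption, 0.80 to 0.95); correlation ρ between an evening entry and the following morning entry (assumption, 0, 0.5 or 1); days independent of each other (assumption).

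- Mornings-only rule: P(X ≥ 10), X ~ Binomial(14, p).
- Paired rule: P(Y ≥ 10), Y ~ Binomial(14, π), with π = p² + ρ·p(1 − p).

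For p = 0.85, π = 0.7225 at ρ = 0, and π = 0.7225 + 0.5 × 0.1275 = 0.786 at ρ = 0.5.

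Probability that a morning-only 2-week value survives:

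| p | Paired, ρ = 0 | Paired, ρ = 0.5 | 10 of 14 mornings |
|---|---|---|---|
| 0.95 | 0.99 | 1.00 | 1.00 |
| 0.90 | 0.89 | 0.96 | 0.99 |
| 0.85 | 0.66 | 0.84 | 0.95 |
| 0.80 | 0.39 | 0.65 | 0.87 |

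At ρ = 1, π = p and the two rules agree.

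Every period that passes the paired rule also passes the mornings-only rule. The excess loss, meaning a period rejected despite at least 10 mornings, is therefore the difference between the two survival probabilities:

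| p | ρ = 0 | ρ = 0.5 | ρ = 1 |
|---|---|---|---|
| 0.95 | 0.8% | 0.2% | 0% |
| 0.90 | 10.0% | 3.2% | 0% |
| 0.85 | 29.6% | 11.4% | 0% |
| 0.80 | 47.8% | 22.1% | 0% |

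**Baseline.** Inclusion Criterion 7 requires at least 70% diary adherence in the 14 days before SV4. Since 0.70 × 14 = 9.8, that means 10 days, the same threshold. The paired definition of an adherent day is worded there only for SV1 to SV2, so carrying it into the SV4 window is an inference. If it carries over, the baseline rule should rarely remove anyone.

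**The case against.** The pairing looks deliberate. The diary day runs from evening to the next morning across the 2-weekly endpoints, Inclusion Criterion 7 uses the same pairing to define adherence, and 70% of 14 days gives the same 10. One threshold for all 2-weekly variables is a defensible convention, and it keeps the daytime, night-time and total symptom means on the same participant-periods. This stands as an explanation of the rule. It does not give a reason to discard a fully observed awakenings record.

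The reach is also narrow, and this stands. A reader might infer that the diary endpoints in general lose valid data. They do not. The symptom outcome variable is the daily total and rescue use is in puffs per day, so both need both entries. SAP 3.1.1 describes the 2-weekly PEF analysis as using morning and evening values. Awakenings are the only protocol-listed endpoint clearly affected. The separate symptom means are an SAP addition, and the output list in SAP Appendix C names no table specific to them.

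A reader might also take the 0.39 figure as the likely loss. It needs p = 0.80 and independent misses, which implies 0.80² = 64% paired days, or 0.64 × 14 ≈ 9 days. That is below the 70% paired adherence required between SV1 and SV2, so a typical participant of that kind would not have been randomised. Adherence may fall later, but it is assessed at every scheduled visit from SV4 to SV12.

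Finally, a reader might infer that the analysed sample becomes selective or biased. The documents do not show this. The rule removes a 2-week period, not a participant. The model spans 12 post-baseline periods, so other periods still contribute, and nothing points to a difference between arms.

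**Conclusion.** The mismatch is certain on the text. SAP 3.1.1 and 3.1.4 can set to missing a 2-weekly value whose own entries are complete, for night-time awakenings and for the two supplementary single-entry symptom means. All three are exploratory. The primary and secondary endpoints are untouched, and CompEx has its own baseline minimum of 7 days.

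The size cannot be derived from the documents. It depends on assumed completion and on how often evening and morning entries are missed together. It is negligible at 95% completion, material at 80% to 85% unless misses largely coincide, and zero if they always coincide. Any loss should fall mainly after baseline. The point is a cheap gain in precision that fits the plan's aim of using the available data. It does not show bias and does not bear on the trial's main conclusions.

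**What to change.** In SAP 3.1.1 and 3.1.4, keep the threshold of 10 of 14 and specify what is counted for each variable:

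- Morning entries only for night-time awakenings and the night-time symptom mean.
- Evening entries only for the daytime symptom mean.
- Evening-plus-morning pairs, unchanged, for the symptom total, daily rescue puffs, and home PEF and FEV1. Naming home PEF and FEV1 avoids leaving them without a minimum.

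The cost is a wording edit in two sections and a small programming change, with no new data collection. One small downside is that the daytime, night-time and total symptom means may rest on slightly different participant-periods, which a table footnote can state. If the uniform paired rule is preferred, the SAP should say that it is meant to apply to single-entry variables as well.

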Physical examination	X ^b		X ^b	X ^c	X ^c					
Weight	X						X		X	X
Vital signs	X		X	X	X	X	X	X	X	X
ECG	X ^d						X		X	X
Echocardiogram ^e						X ^f				
Assessment of AEs/SAEs	X	X	X	X	X	X	X	X	X	X
Injection site reactions	X		X	X	X	X	X			X
SARS-CoV-2 PCR test ^g	X		X	X	X	X	X	X	X	X
Collect blood^h for:										
Haematology	X		X	X	X	X	X		X	X
Coagulation parameters	X		X	X	X	X	X		X	X
Serum chemistry	X		X	X	X	X	X		X	X

Table 2 Schedule of Activities: Study Intervention and Follow-up Periods

Period	Study Intervention							Follow-up		
Visit Number	SV4 (Randomisation)	SV5 (TC)	SV6	SV7	SV8	SV9	SV10	SV11	SV12	E/D
Study Day	1	2	8 (± 3)	29 (± 3)	57 (± 3)	85 (± 3)	113 (± 3)	141 (± 3)	169 (± 3)	
Study Week	0	0	1	4	8	12	16	20	24	
NT-proBNP ^e					X	X	X		X	X
PK (serum)	X		X	X	X	X	X	X	X	X
Immunogenicity (serum)	X		X	X	X	X	X		X	X
Exploratory biomarkers (serum)	X		X	X	X	X	X	X	X	X
SARS-CoV-2 serology test (serum)	X						X			X
Total IgE (serum)	X						X		X	
Allergen-specific IgE (serum)	X									
EDN (plasma)	X			X			X		X	
sST2 (serum)	X						X			
RNA PAXgene	X						X			
CCI [REDACTED]	CI									
CCI [REDACTED]	CI									
DNA for exploratory genetics evaluation (optional)	X ⁱ									
Collect urine for:										
Urinalysis	X		X	X	X	X	X			X
Pregnancy test ^j	X			X	X	X	X		X	X

Table 2 Schedule of Activities: Study Intervention and Follow-up Periods

Period	Study Intervention							Follow-up		
Visit Number	SV4 (Randomisation)	SV5 (TC)	SV6	SV7	SV8	SV9	SV10	SV11	SV12	E/D
Study Day	1	2	8 (± 3)	29 (± 3)	57 (± 3)	85 (± 3)	113 (± 3)	141 (± 3)	169 (± 3)	
Study Week	0	0	1	4	8	12	16	20	24	
Collect nasal sample for:										
Nasal mucosal sampling (lining fluid)	X			X	X	X	X	X	X	
Nasal mucosal sampling (mRNA) ^k	X						X			
Verify eligibility criteria	X									
Randomisation	X									
Study intervention administration^l	C			C	C	C				
Pandemic impact assessment^m	X	X	X	X	X	X	X	X	X	X
Exploratory cough sub-study only										
At-home cough monitoring (for the 24 hours post-clinic visit)							X			
Cough VAS							X			

^a Airway oscillometry and spirometry performed 4 hours (± 15 minutes) post administration of study intervention will require 4 hours withhold of bronchodilator (see Section 6.5.3).

^b Brief physical examination.

^c Complete physical examination.

^d Triplicate ECG. The mean value of each parameter from the triplicate will be used as the baseline value.

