It is recognised that depending on the location and facilities of a clinical site, study visit attendance may place participants at risk of exposure to SARS-CoV-2. Furthermore, it is recognised that more general population-level measures to reduce infection rates (eg, travel restrictions) may inhibit the ability of participants to attend study visits. Necessary healthcare responses at sites to the pandemic (eg, additional infection control measures) may also inhibit the ability of a clinical site to effectively and properly conduct the study. Study visit attendance for dosing and for clinical assessments of treatment response are critical for the scientific value of the study.

Therefore, investigators should not enrol participants unless they have reasonable confidence that throughout the duration of the study:

- Participants will be able to attend study visits, whilst avoiding contact with concentrations of COVID-19 patients (eg, hospital entrances used by such patients); and
- The site will be able to conduct the study effectively and safely, considering relevant national and local factors.

The primary endpoint will be analysed using a repeated measures mixed effect model which, in the event of missing data, uses all data that are available. The sponsor will monitor the number of discontinuations, withdrawals, missed visits and other missing data.

AstraZeneca will routinely conduct risk-based enrolment assessments on a country and site level during the pandemic phase of COVID-19, and study monitoring will focus, in part, on AEs associated with new onset SARS-CoV-2 infection and participants withdrawn due to COVID-19 illness.

All site staff should wear personal protective equipment in accordance with local or national guidelines.

If, for reasons related to the COVID-19 pandemic, a participant is not able to attend their scheduled visit within the ± 3 day visit window, they can have their visit rescheduled within 14 days of the original scheduled visit; however, visits that cannot be rescheduled within a 14 day window must be skipped and participants should continue at the next scheduled visit.

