- During the intervention period, participants will be required to take their asthma controller therapy regularly, complete the eDiary and perform lung function tests using a spirometry device at home regularly.
- An automated alert to the participant and site will be triggered if there is a clinically significant deterioration in any of the eDiary data points (as defined in Section 8.1.5) for > 2 days, prompting the participant to contact the investigator for further assessment of a possible asthma exacerbation. Alerts will only be received by site when eDiary uploads/syncs on adequate mobile or broadband signal; therefore, participants may initiate contact with the investigator for assessment of possible exacerbation regardless of any prompts from the site, or the eDiary and spirometry.

Follow-up Period

- Participants who complete the 16-week intervention period visit will complete an 8-week post-treatment follow-up period.
- Participants will be required to take their SOC asthma controller medications throughout the follow-up period.

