Table 4 Analysis visit windows for ACQ-6, haematology, coagulation parameters, serum chemistry and immunogenicity

Protocol Visit	Week	Analysis Visit	Scheduled Study Day	Visit Window for Analysis (Days)
SV4	Week 0	Baseline	1	All assessments prior to the first administration of investigational product
SV6	Week 1	Week 1	8	All assessments on or after the first administration of investigational product to Day 19
SV7	Week 4	Week 4	29	20 to 43
SV8	Week 8	Week 8	57	44 to 71
SV9	Week 12	Week 12	85	72 to 99
SV10	Week 16	Week 16	113	100 to 141
SV12	Week 24	Week 24	169	≥142

SV = Study Visit.

Table 5 Analysis visit windows for SNOT-22, Airwave Oscillometry and urinalysis

Protocol Visit	Week	Analysis Visit	Scheduled Study Day	Visit Window for Analysis (Days)
SV4	Week 0	Baseline	1	All assessments prior to the first administration of investigational product
SV6	Week 1	Week 1	8	All assessments on or after the first administration of investigational product to Day 19
SV7	Week 4	Week 4	29	20 to 43
SV8	Week 8	Week 8	57	44 to 71
SV9	Week 12	Week 12	85	72 to 99
SV10	Week 16	Week 16	113	≥100

SV = Study Visit.

Table 6 Analysis visit windows for SGRQ

Protocol Visit	Week	Analysis Visit	Scheduled Study Day	Visit Window for Analysis (Days)
SV4	Week 0	Baseline	1	All assessments prior to the first administration of investigational product
SV7	Week 4	Week 4	29	All assessments on or after the first administration of investigational product to Day 57
SV9	Week 12	Week 12	85	58 to 99
SV10	Week 16	Week 16	113	100 to 141
SV12	Week 24	Week 24	169	≥142

SV = Study Visit.

Table 7 Analysis visit windows for NT-proBNP assessment

Protocol Visit	Week	Analysis Visit	Scheduled Study Day	Visit Window for Analysis (Days)
SV4	Week 0	Baseline		All assessments prior to the first administration of investigational product
SV8	Week 8	Week 8	57	All assessments on or after the first administration of investigational product to Day 71
SV9	Week 12	Week 12	85	72 to 99
SV10	Week 16	Week 16	113	100 to 141
SV12	Week 24	Week 24	169	≥142

SV = Study Visit.

Table 8 Analysis visit windows for ECGs and total IgE (serum)

Protocol Visit	Week	Analysis Visit	Scheduled Study Day	Visit Window for Analysis (Days)
SV4	Week 0	Baseline	1	All assessments prior to the first administration of investigational product
SV10	Week 16	Week 16	113	All assessments on or after the first administration of investigational product to Day 141
SV12	Week 24	Week 24	169	≥142

SV = Study Visit.

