3.5.2 Vital signs variables

Vital signs assessments (body temperature, diastolic blood pressure (DBP), systolic blood pressure (SBP), heart (pulse) rate and respiratory rate) will be performed at visits SV1, SV4, SV6, SV7, SV8, SV9, SV10, SV11, SV12 and E/D. For SV4 and SV7 vital signs will be taken before and immediately after administration of study intervention, and at 30, 60, and 120

minutes (± 5 minutes). For SV8 and SV9 vital signs will be taken before and immediately after administration of study intervention, and at 30 and 60 minutes (± 5 minutes) thereafter.

Height will be assessed at SV1 only. Weight will be assessed at SV1, SV4, SV10, SV12 and E/D.

Body mass index will be calculated from the height (in meters) and weight (in kilograms) as follows: $BMI = \text{weight} / (\text{height}^2)$.

Additionally, vital signs values will be classified as normal (if value is between lower and upper limit), low (if value is below the lower limit), and high (if value is above the upper limit) according to the normal reference ranges (Table):

Table 17 Vital sign reference ranges

Parameter	Standard Unit	Lower limit	Upper limit	Change Criteria
Body temperature	$^{\circ}\text{C}$		>37	± 1
DBP	mmHg	<60	>100	± 15
SBP	mmHg	<90	>160	± 30
Heart (pulse) rate	beats/min	<50	>100	± 20
Respiratory rate	breath/min	<12	>24	± 3
BMI	kg/m^2	<18.5	≥ 35	

High value (H) is defined as upper reference limit. High change (HC) is defined as increase from baseline greater than prespecified criterion. Low value (L) is defined as below lower reference limit. Low change (LC) is defined as decrease from baseline greater than prespecified criterion.

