3.5.4 Electrocardiogram (ECG)

ECG variables will be collected at visits SV1, SV4, SV10, SV12, and E/D as follows:

- Heart (pulse) rate
- RR interval
- QRS interval

- PR interval
- QT interval

Additionally, QT correction using Bazett's and Fridericia's formulas will be calculated as follows (unless already derived directly from the CRF):

$$QTcB = QT/(RR^{1/2}),$$

$$QTcF = QT/(RR^{1/3}),$$

where QT is measured in msec and RR is measured in sec.

Categorical ECG interpretation (normal, abnormal clinically significant, abnormal not clinically significant) will be provided by the investigator.

Table 19 ECG reference ranges

Parameter	Standard Unit	Lower limit	Upper limit	Change criteria
Heart (pulse) rate	beats/min	<50	>100	
RR interval	ms	<600	>1200	
QRS interval	ms	<80	>120	
PR interval	ms	<120	>200	
QT interval	ms	N/A	>450 male >470 female	+30
QTcB interval	ms	N/A	>450 male >470 female	+30
QTcF interval	ms	N/A	>450 male >470 female	+30

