4.2.7.4 Analysis of ECG

ECG variables will be summarised with descriptive statistics at each visit and change from baseline summarised for each post-baseline visit by treatment group and for total MEDI3506. Investigators' ECG assessments at baseline versus last observation on treatment will be summarised in shift table by treatment group and for total MEDI3506. Key subject information will be produced for ECG parameter values outside predefined criteria (Table).

In addition, the number and percentage of participants with QTcF intervals (derived as described in Section 3.5.4) at any observation on treatment >450 ms, >480 ms, >500 ms and QTcF increase from baseline >30 ms, >60 ms, >90 ms, and combination of both, will be presented by treatment group and for total MEDI3506.

Individual ECG results and abnormalities in ECG will be listed.

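### The on-treatment cut-off leaves no room for visit windows, so a compliant Week 16 ECG can drop out of the ECG shift and QTcF outlier tables

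*SAP*

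**What the plan says.** **Phase rule.** The study phase windows in SAP 3.1.4 carry the on-treatment phase from Day 1 "to last dose date plus 28 days (included"; later assessments are follow-up. The section says the phases serve mainly the safety and CompEx analyses.

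**Dosing and visits.** In Protocol 1.3, Table 2, the row "Study intervention administration" has entries only under SV4, SV7, SV8 and SV9. SAP 3.5.2 confirms SV9 as a dosing visit: "For SV8 and SV9 vital signs will be taken before and immediately after administration of study intervention". SV9 is Day 85 ±3 and SV10 is Day 113 ±3. Table 2 puts SV10 among the intervention visits, and Protocol 4.1 starts follow-up after it: "Participants who complete the 16-week intervention period visit will complete an 8-week post-treatment follow-up period".

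**ECG schedule and tables.** SAP 3.5.4 states "ECG variables will be collected at visits SV1, SV4, SV10, SV12, and E/D as follows". Baseline is the pre-dose triplicate at SV4. SAP 4.2.7.4 says that investigators' "ECG assessments at baseline versus last observation on treatment will be summarised in shift table", and restricts the QTcF threshold counts to on-treatment observations as well. For by-visit summaries, SAP 3.1.4, Table 8, instead assigns to Week 16 "All assessments on or after the first administration of investigational product to Day 141".

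**Rescheduling.** For participants unable to attend within the window because of COVID-19, Protocol 2.3.1.2 says "they can have their visit rescheduled within 14 days of the original scheduled visit".

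**The concern.** The cut-off falls exactly on the nominal Week 16 day and ignores the ±3-day windows at both visits. A slightly early SV9 or a slightly late SV10, each allowed, moves the Week 16 ECG into follow-up. The same ECG is then Week 16 in the by-visit summary and absent from the two tables restricted to treatment.

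ECG is where this matters most, because it is measured so rarely. Between the SV4 baseline and SV12 (Week 24) a completer has one scheduled ECG, at SV10. If that one is reclassified and there is no unscheduled ECG, the participant has no post-dose value in either table. A QTcF above 500 ms at a fully compliant Week 16 visit could be missing from the table built to count it. SAP Appendix C lists no follow-up QTcF outlier table that would pick it up.

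Other outputs lose less. The laboratory shift tables and the on-treatment ALT/AST by bilirubin table still have Weeks 1, 4, 8 and 12. The NT-proBNP shift table still has Weeks 8 and 12.

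**Working it through.** **Inputs.** SV9 Day 85 ±3 and SV10 Day 113 ±3 (Protocol 1.3, Table 2); cut-off of 28 days, inclusive (SAP 3.1.4); COVID-19 rescheduling of up to 14 days (Protocol 2.3.1.2).

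**The plan's figure.** Nominal gap = 113 − 85 = 28 days, equal to the cut-off.

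**Compliant range.** Shortest gap: 110 − 88 = 22 days. Longest: 116 − 82 = 34 days. Gaps of 29 to 34 days are classed as follow-up.

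**Share affected.** Let d9 and d10 be the deviations in days from the scheduled day. The gap is 28 + d10 − d9, so the ECG falls outside the phase when d10 > d9. If the deviations are independent with the same distribution, the share is (1 − P(d9 = d10)) / 2. The documents do not say how visit days are distributed, so each row below is an assumption. All apply to participants dosed at SV9 who attend SV10.

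| Assumption | Calculation | Share beyond 28 days |
|---|---|---|
| Uniform, ±1 day | 3/9 | 33.3% |
| Uniform, ±2 days | 10/25 | 40.0% |
| Uniform, ±3 days | 21/49 | 42.9% |
| 70% on the exact day at each visit, rest even over ±1 to ±3 | (1 − 0.49 − 6 × 0.05²)/2 | 24.8% |
| 90% on the exact day at each visit, rest even over ±1 to ±3 | (1 − 0.81 − 6 × (0.1/6)²)/2 | 9.4% |
| SV9 uniform ±3; SV10 days +1 to +3 at double weight | [(0+1+2+3) + 2 × (4+5+6)]/(7 × 10) = 36/70 | 51.4% |
| Same deviation at both visits in half of participants, otherwise uniform ±3 | 0.5 × 42.9% | 21.4% |

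If the chance of an outlier does not depend on the visit day, each share is also the chance that a single Week 16 QTcF outlier is missing from the table.

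**COVID-19 rescheduling.** SV10 can move to Day 113 + 14 = 127. With SV9 on Day 82 the gap is 127 − 82 = 45 days, 17 beyond the cut-off. Moving SV9 works the other way: SV9 on Day 85 + 14 = 99 with an in-window SV10 gives gaps of 110 − 99 = 11 to 116 − 99 = 17 days.

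**A longer fixed cut-off.** Of the 49 allowed SV9/SV10 day pairs, 21 lie beyond 28 days, 6 beyond 31 days (12.2%) and none beyond 34 days.

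**The case against.** - **The exclusion is inferred.** SAP 4.2.7.4 does not refer back to 3.1.4, whereas the adverse event sections do. The phase rule names only laboratory data and adverse events as examples, and 3.1.4 makes analysis visit windows the default for safety analyses. This shows the wording is not airtight. But 3.1.4 holds the SAP's only definition of on-treatment and applies it to safety analysis. If ECG is meant to be exempt, the SAP has to say so.
- **The data survive elsewhere.** The by-visit summaries and listings keep the value, and so does the key subject information for ECG values outside predefined criteria, which has no on-treatment restriction. An individual extreme QTcF would be visible there. The windows are the same in every blinded arm, so no bias between arms is expected. Protocol 9.4.4 itself commits only to by-visit ECG summaries. All of this stands. It limits the harm to the counts in two tables but does not make those counts complete.
- **The shares are assumed.** This is also true. Exact-day attendance would give zero, and combining 90% exact-day attendance with shared deviations in half of participants gives 0.5 × 9.4% = 4.7%. The percentages are scenarios, not bounds.
- **The 28-day rule looks deliberate.** It equals the SV8-to-SV9 spacing (85 − 57 = 28) and is also used for exposure, CompEx and exacerbation rates. A second rule means that an ECG finding on day 30 after the last dose would be on treatment while an adverse event starting that day would not be treatment-emergent. That is a real cost and needs a footnote.

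**Conclusion.** The concern holds and should be corrected. The mechanism is exact date arithmetic: a compliant SV10 visit 29 to 34 days after the SV9 dose is classed as follow-up, although the protocol puts SV10 in the intervention period and SAP Table 8 calls its ECG Week 16. An affected completer without an unscheduled ECG has no post-dose value in the ECG shift or QTcF outlier table.

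The main scenarios put this at about 9 to 51 per 100 participants dosed at SV9 and seen at SV10. The true share could be lower if attendance is very punctual or SV10 is booked from the actual SV9 date. COVID-19 delays to SV10 would raise it and delays to SV9 would lower it.

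The primary endpoint and the efficacy comparisons are not touched. What is at stake is the completeness of two safety tables, and an unstated denominator that depends on which permitted day the visit fell.

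**What to change.** Add to SAP 3.1.4, for ECG, laboratory and NT-proBNP outputs restricted to the treatment period only:

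> *For participants dosed at SV9, the on-treatment phase ends at the later of 28 days after the last dose and the SV10 visit date. If SV10 is not attended, or the participant was not dosed at SV9, it ends 28 days after the last dose.*

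This keeps every in-window SV10 assessment and those rescheduled for COVID-19. If a cap is wanted for very late SV10 visits, the Table 8 limit of Day 141 is available for ECG. Leave the 28-day rule unchanged for CompEx, exacerbation rates, exposure and treatment-emergent adverse events; if the phase is changed globally instead, reconcile those sections explicitly. Add a cross-reference to 3.1.4 in SAP 4.2.7.4. In both ECG tables, use as the denominator the number of participants with a post-dose on-treatment ECG.

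Two simpler options are weaker. A fixed cut-off of 34 days covers in-window visits but not those rescheduled for COVID-19. Including every ECG assigned to Week 16 under Table 8 would also count ECGs taken long after dosing stopped in participants who discontinued early but stayed in the study.

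The cost is one SAP sentence, a second phase-end variable for the visit-based safety datasets, and a footnote on the affected tables. The footnote should state that these outputs run past the adverse event and CompEx phase by up to 6 days for in-window visits (34 − 28) and up to 17 days for a COVID-19-rescheduled SV10 (45 − 28).
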